**CONFIDENTIAL**

209538 (NTHI MCAT-009)  
 Statistical Analysis Plan Amendment 2

Objectives	Endpoints
Secondary	
Descriptive 
 
To evaluate the safety and reactogenicity profile of GSK Biologicals' NTHi-Mcat investigational vaccine when administered 1 or 3 or 6 months after Shingrix vaccine or when administered alone.
 
	
 
Solicited local and general adverse events (AEs)           
 
Occurrence of each solicited local and general adverse event (AE), reported during a 7-day follow-up period (i.e. day of vaccination and 6 subsequent days) after Dose 1 and after Dose 2 of GSK Biologicals' NTHi-Mcat investigational vaccine, in all subjects in all groups.
 
 
 
Unsolicited AEs           
 
Occurrence of any unsolicited AEs, reported during a 30-day follow-up period (i.e. day of vaccination and 29 subsequent days) after Dose 1 and after Dose 2 of GSK Biologicals' NTHi-Mcat investigational vaccine, in all subjects in all groups.
 
 
 
Serious AEs           
 
Occurrence of any SAE reported from first vaccination (Day 1) to Day 331 in all subjects in all groups.
 
Occurrence of any SAE, reported from Day 331 to Day 661 in all subjects in all groups.
 
 
 
Potential immune-mediate diseases (pIMD)           
 
Occurrence of any pIMD, reported from first vaccination (Day 1) to Day 331 in all subjects in all groups.
 
Occurrence of any pIMD, reported from Day 331 to Day 661 in all subjects in all groups.
 
 
 

Descriptive 
 
To describe the humoral immune response of GSK Biologicals' NTHi-Mcat investigational vaccine when administered 1 or 3 or 6 months after Shingrix vaccine or when administered alone.
 
	
 
Humoral response           
 
Anti-PD, anti-PE, anti-PilA and anti-UspA2 antibody concentrations and seropositivity in all subjects before Dose 1 (Day 91; Day 151; Day 241 in the Sh_NTHi-Mcat groups and Day 1 in the NTHi-Mcat group), and 1 month after Dose 2 of NTHi-Mcat vaccine (Day 181; Day 241; Day 331 in the Sh_NTHi-Mcat groups and Day 91 in the NTHi-Mcat group).
 
 
 

Descriptive 
 
To describe the cell mediated immune (CMI) response (CD4+ T-cells) of GSK Biologicals' NTHi-Mcat investigational vaccine when administered 1 or 3 or 6 months after Shingrix vaccine or when NTHi-Mcat is administered alone, in the CMI response sub-cohort.
 
	
 
CMI response           
 
NTHi-specific and Mcat-specific CMI responses as measured by flow cytometry ICS (frequency of specific CD4+ T-cells expressing at least 2 different markers among CD40 ligand (CD40L), interleukin (IL)-2, IL-13, IL-17, interferon gamma (IFN-<math>\gamma</math>), tumour necrosis factor alpha (TNF-<math>\alpha</math>) upon in vitro stimulation) before Dose 1 (Day 91; Day 151; Day 241 in the Sh_NTHi-Mcat groups and Day 1 in the NTHi-Mcat group), and 1 month after Dose 2 of NTHi-Mcat vaccine (Day 181; Day 241; Day 331 in the Sh_NTHi-Mcat groups and Day 91 in the NTHi-Mcat group) in the CMI response sub-cohort.
 
 
 

**CONFIDENTIAL**

209538 (NTHI MCAT-009)  
 Statistical Analysis Plan Amendment 2

Objectives	Endpoints
Tertiary	
Descriptive 
 
To describe the CMI response (CD8+ T-cells) of GSK Biologicals' NTHi-Mcat investigational vaccine when administered 1 or 3 or 6 months after Shingrix vaccine or when NTHi-Mcat is administered alone, in the CMI response sub-cohort.
 
To explore the T-helper profile of the PD-, PE-, PilA-, UspA2-specific CD4+/ CD8+ T cell responses.
 
	
 
CMI response           
 
NTHi-specific and Mcat-specific CMI responses as measured by flow cytometry ICS (frequency of specific CD8+ T-cells expressing at least 2 different markers among CD40L, IL-2, IL-13, IL-17, IFN-<math>\gamma</math>, TNF-<math>\alpha</math> upon in vitro stimulation) before Dose 1 (Day 91; Day 151; Day 241 in the Sh_NTHi-Mcat groups and Day 1 in the NTHi-Mcat group), and 1 month after Dose 2 of NTHi-Mcat vaccine (Day 181; Day 241; Day 331 in the Sh_NTHi-Mcat groups and Day 91 in the NTHi-Mcat group) in the CMI response sub-cohort.
 
 
 
T-helper profile           
 
T-helper profile of the specific T-cell response in T-helper 1, T-helper 2 and T-helper 17 based on the specific expression of respectively IFN-<math>\gamma</math>, IL-13 and IL-17 before Dose 1 of the NTHi-Mcat investigational vaccine (Day 91; Day 151; Day 241 in the Sh_NTHi-Mcat groups and Day 1 in the NTHi-Mcat group), and 1 month after Dose 2 of NTHi-Mcat investigational vaccine (Day 181; Day 241; Day 331 in the Sh_NTHi-Mcat groups and Day 91 in the NTHi-Mcat group) in the CMI sub-cohort. Frequencies of specific CD4+/CD8+ T cells per 10^6 cells expressing combinations of cytokines/activation markers will be explored.
 
 
 

 Given the different intervals between vaccines, the label for study visits or contacts varies between treatment groups and as such the Visit/contact label varies. Please refer to the study design diagram ([Figure 1](#)).

 A descriptive analysis where the 95% confidence intervals around the geometric mean concentration (GMC) ratio of the Sh\_NTHi-Mcat\_6 group will be presented with all available data. The descriptive analysis may be used to support the interval between Shingrix and NTHi-Mcat vaccines administration

 A descriptive analysis where the 95% confidence intervals around the geometric mean concentration (GMC) ratio of the Sh\_NTHi-Mcat\_6 and Sh\_NTHi-Mcat\_3 groups will be presented with all available data. The descriptive analysis may be used to support the interval between Shingrix and NTHi-Mcat vaccines administration

 Cut-off for seropositivity will be the lower limit of quantification (LLOQ) of the assay.

 Refer to Section 5.3.1 of the study protocol for details regarding the CMI sub-cohort.

**CONFIDENTIAL**209538 (NTHI MCAT-009)  
Statistical Analysis Plan Amendment 2

## 4. ANALYSIS SETS

### 4.1. Definition

Analysis Set	Description
Enrolled	All subjects who signed informed consent
Exposed (ES)	All subjects who received at least 1 dose of the study treatment. The allocation in a group is done in function of the administered treatment.
Full analysis (FAS)	All subjects who received at least 1 dose of the study treatment and have post-vaccination immunogenicity data
Modified full analysis (mFAS)	All subjects who received full study treatment course to which they are randomized and have post-vaccination immunogenicity data
Per protocol (PPS)	All subjects who received full study treatment course to which they are randomized and have post-vaccination data (mFAS) minus subjects with protocol deviations that lead to exclusion
Unsolicited safety	All subjects who received at least 1 dose of the study treatment  (exposed set) that report unsolicited AEs or that report not having unsolicited AEs
Solicited safety	All subjects who received at least 1 dose of the study treatment  (exposed set) who have solicited safety data

 Study treatment refers to the NTHi-Mcat vaccine. Please refer to Section 4.1.1 for additional details.

#### 4.1.1. Additional considerations

The Enrolled set includes all subjects who signed informed consent, excluding subjects withdrawn prior to randomization (e.g. screening failures).

For the Unsolicited and Solicited safety sets, 1 dose of the study treatment refers to the administration of at least 1 dose of the NTHi-Mcat vaccine, in line with the study analysis of solicited and unsolicited AEs. In addition, subjects exposed to *Shingrix* only (if any) will be included in an extra group named “*Shingrix* only” for the safety analyses based on the Exposed Set (ES). Refer to Section 9.1.2 for more details about the algorithm to attribute subjects to groups for the purpose of safety analyses.

### 4.2. Criteria for eliminating data from Analysis Sets

Elimination codes are used to identify subjects to be eliminated from analysis. Details are provided below for each set.

#### 4.2.1. Elimination from Exposed Set (ES)

Code 1030 (study vaccine not administered at all), code 800 (fraudulent data) and code 900 (invalid informed consent) will be used for identifying subjects eliminated from the ES.

**CONFIDENTIAL**

209538 (NTHI MCAT-009)  
 Statistical Analysis Plan Amendment 2

Subjects assigned to code 1030.b (not administering any NTHi-Mcat vaccine), but not to code 1030 will be identified as subjects belonging to the “Shingrix only” group.

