
 To demonstrate the non-inferiority (NI) of the humoral immune response 1 month after Dose 2 of GSK Biologicals' NTHi-Mcat investigational vaccine when administered 1 month after Shingrix vaccine versus the humoral immune response 1 month after Dose 2 of GSK Biologicals' NTHi-Mcat investigational vaccine alone. 	
Humoral immune response
 
Anti-PD, anti-PE, anti-PilA and anti-UspA2 antibody concentrations 1 month after Dose 2 of NTHi-Mcat vaccine in the Sh_NTHi-Mcat_1 group (Day 181) compared to antibody concentrations 1 month after Dose 2 in the NTHi-Mcat group (Day 91).¹

CONFIDENTIAL209538 (NTHI MCAT-009)
Protocol Amendment 1 Final

Objectives	Endpoints

Criterion:
 
Lower limit (LL) of the 2-sided 95% confidence interval (CI) of the geometric mean concentration (GMC) ratio (Sh_NTHi-Mcat/NTHi-Mcat) is above a limit of 0.667 for all anti-PD, anti-PE, anti-PilA, anti-UspA2.
	
Secondary	

Descriptive
 
 To evaluate the safety and reactogenicity profile of GSK Biologicals' NTHi-Mcat investigational vaccine when administered 1 or 3 or 6 months after Shingrix vaccine or when administered alone. 	
 Solicited local and general adverse events (AEs) 
 Occurrence of each solicited local and general adverse event (AE), reported during a 7-day follow-up period (i.e. day of vaccination and 6 subsequent days) after Dose 1 and after Dose 2 of GSK Biologicals' NTHi-Mcat investigational vaccine, in all subjects in all groups. Unsolicited AEs 
 Occurrence of any unsolicited AEs, reported during a 30-day follow-up period (i.e. day of vaccination and 29 subsequent days) after Dose 1 and after Dose 2 of GSK Biologicals' NTHi-Mcat investigational vaccine, in all subjects in all groups.
	
 Serious AEs 
 Occurrence of any SAE reported from first vaccination (Day 1) to Day 331 in all subjects in all groups. Occurrence of any SAE, reported from Day 331 to Day 661 in all subjects in all groups. Potential immune-mediated diseases (pIMD) Occurrence of any pIMD, reported from first vaccination (Day 1) to Day 331 in all subjects in all groups. Occurrence of any pIMD, reported from Day 331 to Day 661 in all subjects in all groups.

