7.7. Contraindications to subsequent vaccination

Prior to receipt of additional study vaccination, subjects must be evaluated to confirm that they are eligible for subsequent vaccination.

If subjects meet any of the original exclusion/inclusion criteria or the criteria listed below, they should not receive additional vaccinations. Subjects should be encouraged to continue other study procedures at the discretion of the investigator (see Section [8.5.5](#)).

- Subjects who experience any serious adverse event judged to be possibly or probably related to study vaccine or non-study vaccines, including hypersensitivity reactions.
- Subjects who develop any new condition which, in the opinion of the investigator, may pose additional risk to the subject if he/she continues to participate in the study.
- Occurrence of a new pIMD or the exacerbation of an existing pIMD that, in the opinion of the investigator, exposes the subject to unacceptable risk from subsequent vaccination. In such cases, the investigator should use his/her clinical judgement prior to administering the next dose of the vaccine. Refer to Section [12.5.5.1](#) for the definition of pIMDs.

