#### **5.4.2.4. Analysis of SAEs and pIMDs**

The analysis of SAEs and pIMDs will be performed on the Exposed Set (ES).

Analysis of SAEs will include:

- All SAEs from Day 1 to Day 331, from Day 331 to Day 661 and from Day 1 to Day 661.
- Fatal SAEs from Day 1 to Day 331, from Day 331 to Day 661 and from Day 1 to Day 661.
- Related SAEs:
  - To any study vaccine, from Day 1 to Day 331, from Day 331 to Day 661 and from Day 1 to Day 661.
  - To the NTHi-Mcat vaccine, from Day 1 to Day 331, from Day 331 to Day 661 and from Day 1 to Day 661, from the day of the first NTHi-Mcat vaccination up to 1 month following the second dose, from the day of the first NTHi-Mcat vaccination up to 6 months following the second dose and from the day of the first NTHi-Mcat vaccination up to 12 months following the second dose (all groups except “Shingrix only”).
  - To *Shingrix* vaccine, from Day 1 to Day 331, from Day 331 to Day 661 and from Day 1 to Day 661 (all groups except NTHi-Mcat).

Analysis of pIMDs will include all occurrences from Day 1 to Day 331, from Day 331 to Day 661 and from Day 1 to Day 661.

**CONFIDENTIAL**209538 (NTHI MCAT-009)  
Statistical Analysis Plan Amendment 2**5.4.2.5. Other safety analyses**

Medications will be coded using GSKDRUG dictionary.

All collected concomitant medications and vaccinations will be listed. In addition, prior and concomitant vaccinations will be summarized. In case of pregnancies during the study, follow-up data and pregnancy outcomes will be described in detail.

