**9.1.2. Attributing subjects to time-lag groups**

For the purpose of safety analyses, the following rule will be used to attribute exposed subjects to a specific group.

- If a subject receives no *Shingrix* vaccination → NTHi-Mcat group
- If a subject receives at least 1 *Shingrix* vaccination, but no NTHi-Mcat vaccination → “*Shingrix only*” group
- If a subject receives at least 1 *Shingrix* vaccination and at least 1 NTHi-Mcat vaccination, the difference, in days, between the latest *Shingrix* vaccination and the earliest NTHi-Mcat vaccination will be computed and converted in months (diff):
  - diff ≤ 2 → Sh\_NTHi-Mcat\_1 group
  - 2 < diff ≤ 4.5 → Sh\_NTHi-Mcat\_3 group
  - diff > 4.5 → Sh\_NTHi-Mcat\_6 group

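### Safety tables that start at Day 1 leave Shingrix-arm subjects who never receive NTHi-Mcat out of their randomised arm, and the affected period lengthens with the lag

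*SAP*

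**What the plan says.** Three SAP sections set the grouping for safety.

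- SAP 4.1.1: for safety analyses on the Exposed Set, subjects exposed to Shingrix "only (if any) will be included in an extra group named" 'Shingrix only'.
- SAP 4.2.1: "Subjects assigned to code 1030.b (not administering any NTHi-Mcat vaccine), but not to code 1030 will be identified as subjects belonging to the" same group.
- SAP 9.1.2: "For the purpose of safety analyses, the following rule will be used to attribute exposed subjects to a specific group". At least one Shingrix dose and no NTHi-Mcat dose leads to Shingrix only. No Shingrix dose leads to the control group. Everyone else is placed by the gap between the last Shingrix dose and the first NTHi-Mcat dose.

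SAP 5.4.2.4 analyses SAEs and pIMDs on the Exposed Set with windows that open at Day 1, for example "Fatal SAEs from Day 1 to Day 331, from Day 331 to Day 661 and from Day 1 to Day 661". Shingrix-related SAEs and pIMDs use the same windows. SAP 5.4.1 counts AEs leading to withdrawal from first vaccination and names no analysis set for them.

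The protocol's secondary safety endpoint (Section 4, Table 6) is "Occurrence of any SAE reported from first vaccination (Day 1) to Day 331 in all subjects in all groups". Protocol 5.2 defines four groups. For the Exposed Set, Protocol 10.2 and SAP 4.1 both say: "The allocation in a group is done in function of the administered treatment".

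Protocol 7.7 lists conditions under which no further dose should be given. They include "Subjects who experience any serious adverse event judged to be possibly or probably related to study vaccine", and also a new or worsened pIMD, or a new condition, that the investigator judges a risk.

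**The concern.** In the Shingrix arms the counting window opens at the first Shingrix dose, but a subject belongs to a lag group only if NTHi-Mcat is given later. Group membership is therefore fixed by something that happens after counting has begun, and the outcomes being counted can prevent it. A subject who dies, withdraws or is barred from further doses before NTHi-Mcat leaves both the numerator and the denominator of the randomised arm. Controls receive NTHi-Mcat on Day 1 and cannot leave by this route.

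The waiting time is longest in the 6-month arm, so the gap follows the factor under study. The three arms share one Shingrix-only column, so a reader cannot return the events to their arms. Safety by lag is a stated secondary objective, and the Day 1 tables of deaths, SAEs and pIMDs are where a reader would look for it.

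**Working it through.** **1. The plan's own denominator.** Protocol 10.1.2 gives 108 evaluable subjects per group and about 20% loss: 108 / (1 − 0.20) = 135 randomised per group. This reproduces the plan's figure. It is the planned as-randomised denominator that the rule then reduces in the Shingrix arms.

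**2. Time before the first NTHi-Mcat dose.** Dosing days are from Protocol 5.2. Days before the dose = dosing day − 1. The windows are 331 − 1 = 330 days and 661 − 1 = 660 days.

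| Arm | First NTHi-Mcat | Days before | Share of Day 1–331 | Share of Day 1–661 |
|---|---|---|---|---|
| Control | Day 1 | 0 | 0% | 0% |
| Sh_NTHi-Mcat_1 | Day 91 | 90 | 90/330 = 27% | 90/660 = 14% |
| Sh_NTHi-Mcat_3 | Day 151 | 150 | 150/330 = 45% | 150/660 = 23% |
| Sh_NTHi-Mcat_6 | Day 241 | 240 | 240/330 = 73% | 240/660 = 36% |

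**3. Which events move.**
- Deaths before NTHi-Mcat: always.
- AE withdrawals completed before NTHi-Mcat: always out of the Shingrix arm. On the Exposed Set they go to Shingrix only. On the unsolicited safety set, code 1030.b removes the subject altogether (SAP 4.2.5.1.1).
- SAEs and pIMDs before NTHi-Mcat: only if the subject never receives NTHi-Mcat, whether barred under Protocol 7.7 or for any other reason. If NTHi-Mcat is given, the event stays in the arm.

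**4. How large it could be.** The documents give no death, SAE or pre-NTHi-Mcat attrition rates. The 20% allowance covers every cause of non-evaluability. The rates below are therefore assumptions, with constant hazard and 135 per arm.

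Subjects moved = 135 × [1 − (1 − a)^(days before/330)], where a is attrition by Day 331:

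| a | Sh_1 | Sh_3 | Sh_6 |
|---|---|---|---|
| 2% | 0.7 | 1.2 | 2.0 |
| 5% | 1.9 | 3.1 | 4.9 |
| 10% | 3.8 | 6.3 | 10.0 |
| 20% | 8.0 | 13.0 | 20.2 |

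Deaths moved = 135 × [1 − (1 − r)^(days before/365.25)], where r is the annual death rate. The full Day 1–331 expectation uses 330 days:

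| r | Expected per arm | Moved, Sh_1 | Moved, Sh_3 | Moved, Sh_6 |
|---|---|---|---|---|
| 0.5% | 0.61 | 0.17 | 0.28 | 0.44 |
| 1% | 1.22 | 0.33 | 0.56 | 0.89 |
| 2% | 2.44 | 0.67 | 1.12 | 1.78 |

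SAEs: assume 8% of subjects per year have an SAE, which gives 9.8 expected per 135 over Day 1–331. Let f be the fraction of those with an SAE before NTHi-Mcat who never receive it, and e the number moved for that reason. Reported over true proportion = [(9.8 − e)/(135 − e)] / (9.8/135). This moves no one else.

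| f | Sh_1 | Sh_3 | Sh_6 |
|---|---|---|---|
| 10% | 0.97 | 0.96 | 0.93 |
| 25% | 0.93 | 0.89 | 0.83 |
| 50% | 0.87 | 0.78 | 0.65 |

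Worked case, Sh_6 with f = 50%: e = 3.6, and (6.2/131.4) / (9.8/135) = 0.65.

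**The case against.** The strongest case for the plan has four parts.

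**As-treated allocation is the protocol's own rule for the Exposed Set.** This stands. A reader might infer from the endpoint wording and the four defined groups that the SAP contradicts the protocol. It does not, because Protocol 10.2 itself allocates by treatment given. Tables by randomised arm therefore have to be presented as a supplement.

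**The grouping has a rationale.** The objective concerns NTHi-Mcat given 1, 3 or 6 months after Shingrix. A subject never given NTHi-Mcat has no lag, and up to the second Shingrix dose the three arms follow the same schedule. That supports as-treated grouping for windows that start at NTHi-Mcat Dose 1. It does not justify counting from Day 1 in groups whose members must first reach Day 91, 151 or 241.

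**Nothing is hidden or improvised.** This also stands. A reader might take the extra group to be post hoc, but it is in the first SAP of 01 April 2019 and the study started on 23 April 2019. A reader might also think the events vanish. SAEs, deaths and pIMDs appear in the Shingrix-only column, and the Shingrix-related SAE table excludes only the control group. What is lost is the link to the randomised arm. The withdrawal summary by reason (SAP 5.1.1) may give a partial view, but it does not count SAEs, deaths or pIMDs and is not stated to be by randomised arm.

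**Safety is descriptive.** Protocol 10.3.5 and SAP 5.4.1 describe within-group assessment, and SAP 6 makes non-primary comparisons descriptive. This limits the consequence but does not repair the counts.

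Two further inferences are not supported. One is that the Shingrix-only column will be rich in events. Protocol Amendment 1 expected missed visits in the 3- and 6-month arms because of COVID-19 containment, so the column may hold many administrative non-vaccinations. The other is that SAP 9.1.2 mislabels a subject who misses the second Shingrix dose. It labels the interval actually received, which is what as-treated allocation means.

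**Conclusion.** The point holds as an issue in the descriptive safety outputs that should be corrected. Day-1-anchored SAE, fatal SAE, Shingrix-related SAE, pIMD and AE-withdrawal counts leave out of each Shingrix arm those subjects who never receive NTHi-Mcat, and the SAP text plans no SAE, death or pIMD table that puts them back. For deaths and completed withdrawals the exclusion is complete over the first 90, 150 and 240 days, about 27%, 45% and 73% of Day 1–331, against 0 in control. These shares follow from the dosing schedule alone.

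The effect on SAE and pIMD counts is smaller and depends on how many affected subjects go without NTHi-Mcat. A reader might conclude that the trial will show a false fall in deaths or SAEs with longer lag. The rule pushes in that direction, but without event or attrition rates neither the presence nor the size of a visible gradient can be asserted. In the assumed ranges, fewer than two deaths per arm would move, while the reported SAE proportion in the 6-month arm would be 0.65 to 0.93 of the true one. The confirmatory immunogenicity analysis is unaffected.

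**What to change.** In SAP 4.1.1, 4.2.1, 5.4.2.4 and 9.1.2:

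- For safety outputs that start at Day 1 or first vaccination (all SAEs, fatal SAEs, SAEs related to any study vaccine or to Shingrix, pIMDs, AEs leading to withdrawal), add tables by randomised arm that include subjects who received Shingrix but no NTHi-Mcat.
- In those tables, show Shingrix only as an 'of which' row within each randomised arm.
- State that these tables supplement the as-treated Exposed Set allocation in Protocol 10.2 and SAP 4.1 and do not replace it.
- Name the analysis set for AEs leading to withdrawal.
- Keep the treatment-received and lag rule for windows that start at NTHi-Mcat Dose 1: solicited and unsolicited AEs, and the NTHi-Mcat-related SAE windows that run to 1, 6 and 12 months after the second dose.

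The cost is SAP wording, one grouping variable, a few extra tables, and a footnote for any subject given a wrong vaccine sequence. No new data are needed.

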## 4.2.2. Elimination from Full analysis set (FAS)

### 4.2.2.1. Excluded subjects

A subject will be excluded from the FAS analysis under the following conditions:

Code	Condition under which the code is used	Visit (V) (timepoints) where the code is applicable	Applicable for endpoint [HUM=humoral response, CMI=CMI response]
800	Fraudulent data	All	HUM, CMI
900	Invalid informed consent	All	HUM, CMI
1030	Study vaccine not administered at all	All	HUM, CMI
2100.a	Humoral immune response results not available post-vaccination	V6_1, V6_3, V6_6, V4	HUM
2100.b	CMI response results not available post-vaccination	V6_1, V6_3, V6_6, V4	CMI

Note: CMI elimination codes are applicable only to subjects belonging to the CMI sub-cohort.

Note: in case a subject is bled but blood sample is not planned per study protocol (code 2130), the unexpected sample is eliminated from the analysis, but subject is retained.

